4.6 EXPLORATORY ANALYSES

Descriptive statistics will be provided for the exploratory biomarker analyses.

4.7 SAFETY ANALYSES

All safety analyses will be performed on the safety population, unless specified otherwise. All safety data will be summarized using descriptive statistics.

4.7.1 Exposure of Study Medication

Exposure to study treatment will be summarized, with the use of descriptive statistics, on the following:

- Length of time on treatment
- Number of days dosed
- Cumulative dose
- Dose intensity (%) (defined as total amount of study treatment received relative to total amount of study treatment expected between the first and last dose)

Dose modification (dose reduction or interruption) will be summarized as follows:

- n (%) of patients with any dose modification (reduction or interruption)

Dose reduction will be summarized as follows:

- n (%) of patients with at least one dose reduction
- Number of dose reductions per patient (mean, median, and range)
- Final dose level after reduction
- Reasons for change in dose

Dose interruptions will be summarized as follows:

- n (%) of patients with at least one dose interruption
- Number of interruptions per patient (mean, median, and range)

4.7.2 Adverse Events

Safety analyses will include all patients who receive any amount of study treatment (vemurafenib or placebo). Patients who receive any amount of vemurafenib will be summarized in the vemurafenib treatment arm. Safety will be assessed through summaries of all adverse events, including serious adverse events, adverse events of special interest, and adverse events leading to discontinuation of vemurafenib or placebo. All verbatim descriptions of treatment-emergent adverse events will be mapped to MedDRA thesaurus terms and graded according to the NCI CTCAE v4.0.

The following safety parameters will be summarized by treatment arm for patients in Cohort 1 and Cohort 2 separately as well as for all study patients pooled:

- All adverse events
- All adverse events leading to discontinuation of study treatment
- All serious adverse events
- Adverse events of interest (e.g., cutaneous SCC [including KA], QTc prolongation)
- NCI CTCAE Grade 3 or greater adverse events
- Adverse events resulting in death
- All deaths

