Grade 5 adverse events were reported in 6 patients (2%) in the vemurafenib group. Only one adverse event (intracranial tumor hemorrhage) was assessed as treatment related. Each of the other 5 patients experienced the following Grade 5 adverse events (all unrelated to study treatment): general physical health deterioration, cerebrovascular accident, pneumonia, aortic aneurysm rupture, and cardiac failure. Grade 5 adverse events were reported in 8 DTIC-treated patients (3%). Fatigue and mucosal inflammation, initially classified as Grade 5 adverse events in 1 patient, were subsequently considered to be symptoms of disease progression and downgraded to Grade 1, resulting in a total of 7 patients with Grade 5 adverse events. Only one adverse event (shock) was assessed as treatment related. Dyspnea, lung infection, cardiac arrest, and cardiac tamponade were reported in 1 patient each, and cardiopulmonary failure was reported in 2 patients. No Grade 5 adverse events were reported in the 37 patients who crossed over from DTIC to vemurafenib.

The incidence of cuSCC in vemurafenib-treated patients was approximately 20% across studies. The majority of the excised lesions reviewed by an independent central dermatopathology laboratory were classified as SCC-KA subtype or with mixed KA features (52%), both of which are less invasive types of cuSCC. Most lesions classified as “other” (43%) were benign skin lesions (e.g., verruca vulgaris, actinic keratosis, benign keratosis, cyst/benign cyst). cuSCC usually occurred early in the course of

treatment, with a median time to the first appearance of 7–8 weeks. Of the patients who experienced cuSCC, approximately 33% experienced more than one occurrence, with a median time between occurrences of 6 weeks. Cases of cuSCC (including KA) were typically managed with simple excision, and patients generally continued on treatment without dose modification. A risk mitigation plan, including regular dermatologic and head and neck examinations and chest computed tomography (CT) scans, has been established to monitor for and treat SCC (both cutaneous and non-cutaneous) in patients receiving vemurafenib in clinical trials (see Section 5.1.2.3).

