Details about the first anti-cancer therapy given after melanoma recurrence or an occurrence of a new primary melanoma will be captured for all patients in the study.

The final analysis of the primary endpoint of DFS will occur for each cohort after the targeted number of events for each cohort is reached (approximately 120 DFS events for Cohort 1 and approximately 105 DFS events for Cohort 2). There will be no interim analyses of the primary endpoint of DFS.

For each cohort, patients without melanoma recurrence or an occurrence of a new primary melanoma and their physicians will remain blinded until the final DFS analysis for that cohort. Physicians may request unblinding for patients who have documented recurrence or an occurrence of a new primary melanoma for purposes of planning subsequent treatment. Unblinding requires prior approval of the Roche Medical Monitor or designee.

In this adjuvant trial, crossover to vemurafenib treatment will not be allowed for patients receiving placebo because this trial is designed to evaluate adjuvant vemurafenib therapy starting within 4 calendar days after randomization and no later than 94 calendar days after definitive melanoma surgery (i.e., the last surgery required for the treatment or the diagnosis of melanoma).

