4.5.2.4 Post-Treatment Follow-Up Assessments

Patients who complete or discontinue study treatment without a recurrence or an occurrence of a new primary melanoma will continue to be followed with regular physical examinations (every 13 ± 2 weeks) and imaging studies for a maximum of 5 years from Cycle 1, Day 1 or until a melanoma recurrence or an occurrence of a new primary melanoma *or until end of study (see Section 3.2)*, whichever occurs first. All patients will be followed for the occurrence of new primary malignancies, regardless of melanoma recurrence or occurrence of a new primary melanoma, *until end of study (see Section 3.2)*.

See Appendix 1 for the Schedule of Assessments performed during follow-up.

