5.1.2.3.3 Cutaneous Squamous Cell Carcinoma (including Keratoacanthoma) and New Primary Melanoma

For all patients, a complete evaluation of the skin by a designated dermatologist or his or her designee who is experienced in the diagnosis and management of cuSCC/KA will be conducted at baseline (up to 90 days prior to randomization), during study drug treatment period, and post-treatment follow-up according to Section 4.5.2 and Appendix 1. An unscheduled dermatology examination may be performed for investigation of any new skin lesions that are suspected of being cuSCC (including those classified as KA) or new primary melanomas. If a patient develops cuSCC/KA either during or after the study drug administration period, this information must be collected and reported as a non-serious adverse event of special interest to the Sponsor, whether it is deemed related or unrelated to study drug. If a patient develops a new primary melanoma either during or after the study drug administration period, this information must be collected and reported to the Sponsor, whether it is deemed related or unrelated to study drug. The following bullet points detail the required monitoring/management of skin-associated vemurafenib risks:

- A dermatologist or his or her designee who is experienced in the diagnosis and management of cutaneous neoplasms will perform skin evaluations to monitor for cuSCC/KA, new primary melanoma, BCC, and actinic keratosis.
- A complete history of prior dermatologic interventions and medications, cuSCC risk factors (i.e., Fitzpatrick skin type, radiotherapy, sun exposure, immunosuppression, prior SCC, use of tanning beds, and precursor lesions), and prior HPV vaccination must be collected. Refer to Appendix 7 for a list of Fitzpatrick skin phototypes.
- Any suspicious lesions identified at baseline and while on study drug and 26 ± 2 weeks after last dose of study drug must be biopsied and excised and sent for pathological examination.
- Available specimen block/sections should be sent to a Roche-designated central pathology laboratory for confirmation of diagnosis and further molecular characterization.

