4.1.2 Safety Population

The safety population will include all patients who receive at least one dose of study treatment. Patients who receive at least one dose of vemurafenib will be included in the vemurafenib safety population. The safety population will be analyzed according to the patients' safety group.

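### Cutaneous SCC and new primary cancers are tabulated by arm with no analysis window and no cut at later therapy, so tumours arising on a post-recurrence BRAF inhibitor can be counted under placebo and dilute the between-arm difference

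*SAP*

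**What the plan says.** **Analysis.** SAP 4.7.2 introduces its list of summaries with "The following safety parameters will be summarized by treatment arm for patients in Cohort 1 and Cohort 2 separately", and adds a pooled display. The list includes serious adverse events and adverse events of interest, with cuSCC named as an example. The grouping follows treatment received: SAP 4.1.2 says "The safety population will be analyzed according to the patients' safety group", and SAP 4.7.2 says "Patients who receive any amount of vemurafenib will be summarized in the vemurafenib treatment arm". Treatment-emergence appears only in the coding sentence: "All verbatim descriptions of treatment-emergent adverse events will be mapped to MedDRA thesaurus terms". Neither document defines the term or gives an analysis window for these tables.

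**Collection.** Protocol 5.1.2.3.3 says: "If a patient develops cuSCC/KA either during or after the study drug administration period, this information must be collected and reported". This applies whether or not the lesion is thought related to study drug. Protocol 4.5.2.4 says: "All patients will be followed for the occurrence of new primary malignancies, regardless of melanoma recurrence". Protocol 5.1.2.3.5 and 5.3.1 extend that reporting to the end of the study. Protocol 5.2.2 classes new primary malignancies other than cuSCC/KA as serious adverse events, so they enter the serious-event table. Protocol 4.5.2.2 schedules skin examinations at the end-of-treatment visit and at 13 and 26 weeks after the last dose.

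**Later therapy.** Protocol 3.1 records the first anti-cancer therapy after recurrence or a new primary melanoma, and says: "Physicians may request unblinding for patients who have documented recurrence or an occurrence of a new primary melanoma for purposes of planning subsequent treatment". No safety analysis in the SAP uses that record.

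**The concern.** Every patient has a BRAF V600 mutation, and Protocol 5.5.1 notes that vemurafenib is approved in the United States for unresectable or metastatic melanoma. A placebo patient whose disease returns in that form is a plausible candidate for a BRAF inhibitor. If the recurrence happens on study drug, study drug stops (Protocol 3.1), and the 13- and 26-week skin examinations run from the last dose. Protocol 1.2.5 puts the median time to first cuSCC on vemurafenib at 7-8 weeks, so those examinations can fall when lesions from the later drug appear.

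The design expects placebo patients to recur sooner, so such lesions would be added to placebo more often than to vemurafenib, and the between-arm difference would shrink. The risk of new cancers in people rendered surgically free of disease is a central safety question, and the placebo arm exists to supply that contrast.

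The SAP handles the same problem elsewhere. Section 4.4.1 censors DFS for patients given non-protocol anti-cancer therapy without an event, and section 4.7.4 confines the worst laboratory grade to the treatment period. Section 4.7.2 has no counterpart.

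**Working it through.** **Step 1: how many patients could reach later therapy.** The inputs are the planned DFS medians in SAP 2.3: 24 and 40 months (Cohort 1), 7.7 and 13.3 months (Cohort 2). With exponential DFS, S(24) = exp(-ln 2 × 24 / median).

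- Cohort 1: 50.0% placebo, 66.0% vemurafenib (the plan states 50% and 66%).
- Cohort 2: 11.5% and 28.6% (the plan states 12% and 29%).

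The plan's own 2-year rates are reproduced. The proportion R with a DFS event by 2 years is therefore 50.0% placebo and 34.0% vemurafenib in Cohort 1, and 88.5% and 71.4% in Cohort 2.

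**Step 2: cuSCC inputs.**

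- c = 20% on a BRAF inhibitor. Protocol 1.2.5: "The incidence of cuSCC in vemurafenib-treated patients was approximately 20% across studies".
- b = 1% placebo background. This is an assumption; Protocol 1.2.5 gives under 1% for the dacarbazine comparator.
- f = share of patients with a DFS event who then receive a BRAF inhibitor. The documents do not give it, so it is varied.

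**Step 3: formulas.**

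- Placebo observed = b + (1 - b) × R(placebo) × f × c
- Vemurafenib observed = c + (1 - c) × R(vemurafenib) × f × c

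Example at f = 50%:

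- Cohort 1 placebo: 0.01 + 0.99 × 0.500 × 0.50 × 0.20 = 0.0595
- Cohort 1 vemurafenib: 0.20 + 0.80 × 0.340 × 0.50 × 0.20 = 0.2272; difference 16.8 points
- Cohort 2 placebo: 0.01 + 0.99 × 0.885 × 0.50 × 0.20 = 0.0976
- Cohort 2 vemurafenib: 0.20 + 0.80 × 0.714 × 0.50 × 0.20 = 0.2571; difference 16.0 points

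**Step 4: results** (differences taken before rounding). The last column holds the vemurafenib arm at 20%, that is, re-treatment adds no further cuSCC risk there.

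| Cohort | f | Placebo | Vemurafenib | Difference (points) | Difference if re-treatment adds nothing (points) |
|---|---|---|---|---|---|
| Both | 0% | 1.0% | 20.0% | 19.0 | 19.0 |
| 1 | 25% | 3.5% | 21.4% | 17.9 | 16.5 |
| 1 | 50% | 6.0% | 22.7% | 16.8 | 14.1 |
| 1 | 100% | 10.9% | 25.4% | 14.5 | 9.1 |
| 2 | 25% | 5.4% | 22.9% | 17.5 | 14.6 |
| 2 | 50% | 9.8% | 25.7% | 16.0 | 10.2 |
| 2 | 100% | 18.5% | 31.4% | 12.9 | 1.5 |

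The ratio is more sensitive than the difference. At f = 50% with rescue in both arms it falls from 20 to about 3.8 (22.7/6.0) in Cohort 1 and 2.6 (25.7/9.8) in Cohort 2.

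**Step 5: why these are near upper bounds for each f.** The full 20% is applied to every rescued patient. DFS events also include deaths, new primary melanomas and locoregional recurrences, while the approval cited is for unresectable or metastatic disease. Scheduled skin examinations end 26 weeks after the last blinded dose, so a patient who recurs well after completing 52 weeks has none while on later therapy.

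**The case against.** The strongest reply is that no rule in the SAP says these tumours will be counted. Adverse events in general are collected to 28 days after the last dose (Protocol 5.3.1), and routine monitoring stops sooner if other anti-melanoma therapy starts (Protocol 5.1.2.2). If treatment-emergent follows that window, most tumours arising on later therapy drop out. This stands in part: the fault is a missing definition. But the narrow window would also remove the 13- and 26-week cuSCC findings and the late new primaries that the protocol takes care to collect. One reading mixes in the effects of later drugs, and the other discards mandated data.

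A reader might take the tables to be by randomized arm. They are not; they use the safety group. The sentence "Patients who receive any amount of vemurafenib will be summarized in the vemurafenib treatment arm" does not say that the vemurafenib must be study treatment. Taken literally, it could move a placebo patient who later takes commercial vemurafenib into the vemurafenib arm because of something that happened after randomization. Its context is study treatment, so the milder reading is more natural. Since the protocol bars crossover, safety group and randomized arm should then largely coincide. The wording still needs to be settled, because the direction of the bias depends on it.

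It is also fair that rescue uptake is unknown, that the sponsor does not intend to supply vemurafenib after the treatment period (Protocol 4.3.4), that safety analysis here is descriptive, and that a display over all follow-up is legitimate. These points limit the size of the problem and argue for keeping the all-events table. They do not supply the missing cut.

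**Conclusion.** The concern holds as a specification gap that can bias a key safety contrast. Tabulating all collected events as SAP 4.7.2 lists them would mix in tumours arising on later BRAF inhibitors, and more so in the arm expected to recur sooner. It is confined to cuSCC/KA, new primary malignancies and late events reported as related, because collection of other adverse events largely stops at 28 days.

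Under the stated assumptions, at 25-50% uptake, the difference falls by roughly 1 to 3 points from 19. At 50% uptake it falls by about 5 points (Cohort 1) and 9 points (Cohort 2) if re-treatment adds no risk in the vemurafenib arm.

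A reader might infer that the plan hides the adjuvant drug's risk. The documents do not support that. The vemurafenib arm's own rate stays at 20% or more in every scenario. The contrast nearly vanishes only in Cohort 2 at 100% uptake with no added risk on re-treatment. The rationale for Protocol Version 10 reports a separate secondary-malignancy analysis with a cuSCC incidence of about 20% among vemurafenib-treated patients. Nor does the annual reporting of new primaries to the FDA under Protocol 5.5.1 depend on this table.

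**What to change.** In SAP 4.7.2:

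1. Define treatment-emergent, and state the analysis window for cuSCC/KA and new primary malignancies.
2. State that the rule placing patients in the vemurafenib arm refers to vemurafenib given as study treatment.
3. Add a by-arm table of cuSCC/KA, new primary melanoma and other new primary malignancies with onset before the first subsequent anti-cancer therapy of any kind, with exposure-adjusted rates to the same cutoff.
4. Show later onsets in a separate table by first subsequent therapy.
5. Keep the all-events table.

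Confirm that the information recorded on first subsequent therapy under Protocol 3.1 includes its start date; the protocol does not say so.

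The cost is SAP wording and two further displays, from existing data if the start date is recorded. The cut table will have fewer events and shorter follow-up, more so for placebo. Because only the first subsequent therapy is recorded, BRAF inhibitors given in later lines cannot be identified. Cutting at the first therapy of any kind avoids that problem in the main table but not in the table of later onsets.

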After signing informed consent, all eligible patients will undergo screening procedures that include a contrast-enhanced magnetic resonance imaging (MRI) of the brain (or contrast-enhanced CT of the brain if an MRI is not generally available or is contraindicated) and contrast-enhanced CT or MRI of the chest, abdomen, and pelvis. While participating in the study, patients will undergo regular, periodic safety evaluations. Surveillance for tumor recurrence (including physical examination and contrast-enhanced CT or MRI of the chest, abdomen, and pelvis) will be performed

every 13 ± 2 weeks until Week 104. During Years 3, 4, and 5 of the study, physical examination will be performed every 13 ± 2 weeks, and the aforementioned imaging studies will be performed every 26 ± 4 weeks until recurrence of melanoma or an occurrence of a new primary melanoma or *until end* of study (see Section 3.2), whichever occurs earlier.

In addition, all patients will undergo contrast-enhanced MRI of the brain (or CT if MRI is generally not available or is contraindicated) every 52 ± 4 weeks until recurrence of melanoma, occurrence of a new primary melanoma, or *until end* of study (see Section 3.2), whichever occurs earlier. Results of fluorodeoxyglucose–positron emission tomography (FDG-PET) scans alone will not be sufficient for purposes of documenting disease recurrence. Evidence of recurrence must be documented by biopsy of a suspect lesion, except in patients whose suspicious lesions are deemed by the investigator not amenable to biopsy. For patients with an isolated, suspected intracranial recurrence, histologic documentation of recurrence of surgically accessible lesions is highly recommended but not required; for these patients, MRI (or CT if MRI is not generally available or is contraindicated) documentation of recurrent disease is sufficient. Surveillance studies to monitor for melanoma recurrence should use the same imaging modality that was used at screening.

Patients who have had a DFS event do not need additional scans or physical exams for surveillance of melanoma recurrence. These patients are also required to discontinue study drug if it was being administered at the time of final diagnosis of the DFS event. However, these patients must still have a chest CT or MRI for SCC surveillance at 13 ± 2 weeks and 26 ± 2 weeks after the last dose of study drug.

A schedule of assessments is provided in [Appendix 1](#).

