5.1.1 Background: Vemurafenib Risks

The toxicity profile for vemurafenib has been documented from safety data derived from seven studies of over 600 treated patients with locally advanced unresectable or metastatic melanoma. The most common toxicities observed were rash, fatigue, arthralgia, myalgia, headache, nausea, photosensitivity, alopecia, and pruritus. The most common laboratory abnormalities reported as adverse events included elevations of liver function tests (i.e., GGT, alkaline phosphatase, ALT, AST, and bilirubin). The majority of adverse events reported in conjunction with Phase I–III clinical trials were of mild or moderate severity. Approximately one-half of all patients treated with vemurafenib required interruption and/or reduction of dose on at least one occasion, although treatment discontinuation because adverse events has been rare.

Approximately 20% of vemurafenib recipients developed one or more localized cuSCCs (mainly KA type). The majority of these was observed within the first 7–8 weeks of vemurafenib exposure and was not treatment limiting. As with all clinical studies of vemurafenib to date, the risk for cuSCC will be mitigated through the use of a Risk Management Plan as outlined in Section [5.1.2.3](#).

Analysis of ECG data from the Phase II Study NP22657 of vemurafenib in patients with metastatic melanoma revealed a risk of QT interval prolongation without associated clinical symptomatology (as noted in Section [5.1.2.3.7](#)).

Two cases of SCC of the head and neck have been reported in 2 patients treated with vemurafenib in excess of 300 days while enrolled in a clinical trial. In addition, five cases of adenomatous colonic polyps have been reported in patients who received vemurafenib for 2 or more years on a clinical trial. One patient who was participating in the Expanded Access Program was found to have a colonic adenoma after being on vemurafenib for 0.57 years (see Section [1.2.5](#) and the Vemurafenib IB for additional details).

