5.3.1 Adverse Event Reporting Period

Investigators will seek information on adverse events at each patient contact. All adverse events, whether reported by the patient or noted by study personnel, will be recorded in the patient's medical record and on the Adverse Event eCRF.

After informed consent has been obtained **but prior to initiation of study drug**, only serious adverse events caused by a protocol-mandated intervention should be reported (e.g., serious adverse events related to invasive procedures such as biopsies).

After initiation of study drug, all adverse events, regardless of relationship to study drug, will be reported up to and including 28 days after the last dose of study drug. After

this period, investigators should report any deaths, serious adverse events, or other adverse events of concern that are believed to be related to prior treatment with study drug (see Section 5.6). In addition, all new primary malignancies will be reported *until end of study* (see Section 3.2), whether or not a patient has exhibited recurrence of melanoma while in the study.

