2.3 SAMPLE SIZE AND ANALYSIS TIMING

The final primary efficacy endpoint (DFS) analyses for the two cohorts will be conducted according to the procedure specified in Section 4.4.1.

2.3.1 Cohort 1

The final analysis of the primary endpoint of DFS for Cohort 1 will take place when approximately 120 DFS events have occurred, on the basis of the following assumptions:

- Two-sided, stratified log-rank test at the 0.05 significance level

- 80% power
- Median DFS for the control arm of 24 months and estimated median DFS in the vemurafenib treatment arm of 40 months (which corresponds to a hazard ratio [HR] of 0.60)
- 5% annual loss to follow-up for DFS
- No interim analysis

Assuming an accrual rate of 8 patients per month in Cohort 1 and a 17-month ramp-up period to reach steady-state enrollment, approximately 300 patients will be required to be enrolled in Cohort 1 during 43 months and followed for an additional 7 months in order to observe 120 DFS events.

On the basis of the assumptions above, 120 DFS events are projected to occur in Cohort 1 approximately 50 months after the first patient is randomized in this study. At that time, it is projected that median follow-up time will be 21 months in Cohort 1, and the minimum follow-up time (e.g., for the last patient randomized) is projected to be 7 months. Also on the basis of the assumptions of 120 DFS events required and a target HR of 0.60, it is projected that an observed HR of 0.70 or better in the DFS analysis will result in a statistically significant difference between treatment arms (i.e., HR of 0.70 is the minimally detectable difference for that analysis).

A summary of the assumptions and characteristics of the DFS analysis for Cohort 1 is shown in [Table 1](#).

For Cohort 1, on the basis of the assumptions of a target HR of 0.60, 120 DFS events would provide 80% power to detect a 16% absolute increase in the 2-year DFS rate (50% vs. 66%, corresponding to a 40% risk reduction; i.e., HR of 0.60).

2.3.2 Cohort 2

The final analysis of the primary endpoint of DFS for Cohort 2 will take place when approximately 105 DFS events have occurred, on the basis of the following assumptions:

- Two-sided, stratified log-rank test at the 0.05 significance level
- 80% power
- Median DFS for the control arm of 7.7 months and estimated median DFS in the vemurafenib treatment arm of 13.3 months (which corresponds to an HR of 0.58)
- 5% annual loss to follow-up for DFS
- No interim analysis

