4.7.4 Laboratory Data

Laboratory toxicities will be defined on the basis of local laboratory normal ranges and the NCI CTCAE v4.0. Laboratory test results and normal ranges will be converted from local lab to Standard International units for analysis purposes. For each laboratory parameter, the toxicity grade at baseline and the worst toxicity grade during the treatment period will be summarized by treatment arm.

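### Recurrence helps decide how long each arm is observed for ordinary adverse events, and SAP 4.7.2 tabulates percentages with no time-at-risk denominator

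*SAP*

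**What the plan says.** **Collection window.** Protocol 5.3.1, for the period from first dose: "all adverse events, regardless of relationship to study drug, will be reported up to and including 28 days after the last dose". Beyond those 28 days, the same section asks for deaths, serious events and other events of concern believed related to treatment, and for all new primary malignancies until end of study. Protocol 5.1.2.3.3 also requires cutaneous squamous cell carcinoma and keratoacanthoma (cuSCC/KA) to be reported during or after treatment, whether or not related.

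**Stopping drug.** Protocol 3.1, on patients with a DFS event: "These patients are also required to discontinue study drug if it was being administered at the time of final diagnosis of the DFS event". Protocol 4.6.1.1 repeats the requirement by type of event. Treatment is capped at 52 weeks (Protocol 4.3.2.1).

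**Expected recurrence.** Cohort 2 is sized in SAP 2.3.2 on "Median DFS for the control arm of 7.7 months and estimated median DFS in the vemurafenib treatment arm of 13.3 months". Cohort 1 is sized on 24 and 40 months (SAP 2.3.1).

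**Analysis.** SAP 4.7.2: "The following safety parameters will be summarized by treatment arm for patients in Cohort 1 and Cohort 2 separately"; the sentence goes on to include all patients pooled. SAP 4.7 makes all safety analysis descriptive, and SAP 4 gives frequency and percentage as the summary for discrete data. For laboratory data, SAP 4.7.4 says that "the worst toxicity grade during the treatment period will be summarized by treatment arm". SAP 4.7.1 tabulates time on treatment, days dosed and cumulative dose. Neither SAP 4.7 nor Protocol 6.5 links exposure to event frequency through a rate, a common time window or a time-to-first-event summary.

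**The concern.** The trial is designed in the expectation that placebo patients recur sooner. Recurrence stops drug, and stopping drug closes the all-cause window 28 days later. The expected efficacy result therefore shortens observation on placebo. A by-arm percentage then mixes the event rate with the length of observation, and an event with the same rate in both arms would look more frequent on vemurafenib. Toxicity stops on vemurafenib push the other way. The rows affected are all adverse events, serious events, Grade 3 or higher events and events leading to discontinuation. Protocol 3.1 has safety evaluated separately in each cohort, so the Cohort 2 columns, where the expected imbalance is largest, will be read on their own.

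**Working it through.** **1. Does an exponential model match the plan?** SAP 2.3.2 assumes 80% power when "approximately 105 DFS events have occurred", with a "Two-sided, stratified log-rank test at the 0.05 significance level". Schoenfeld: z = (√105 / 2) × |ln 0.58| − 1.96 = 2.79 − 1.96 = 0.83, so power is 79.7%. Exponential 2-year DFS at medians of 7.7 and 13.3 months is 11.5% and 28.6%; the SAP states 12% and 29%. The model is consistent with the plan's own figures.

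**2. Mean observation window.** Let λ = ln 2 / median, L = 364 days = 11.96 months and f = 28 days = 0.92 months. If recurrence is the only reason for stopping early, the mean window is (1 − e^(−λL))/λ + f.

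- Cohort 2 placebo: λ = 0.0900, so 0.659/0.0900 + 0.92 = 8.24 months.
- Cohort 2 vemurafenib: λ = 0.0521, so 0.464/0.0521 + 0.92 = 9.82 months. Shortfall on placebo: 1 − 8.24/9.82 = 16.1%.
- Cohort 1: 11.03 and 11.72 months, shortfall 5.9%.
- Pooled, weights 175 and 300: 10.00 and 11.02 months, shortfall 9.2%.

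The numerators 0.659 and 0.464 are the expected proportions with a DFS event by week 52 in Cohort 2. Adding the planned 5% annual loss to both arms changes the Cohort 2 figure to 15.9%.

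**3. Effect on a percentage.** For an event with constant monthly rate r in both arms, P(at least one) = 1 − e^(−rf) × [λ/(λ+r) × (1 − e^(−(λ+r)L)) + e^(−(λ+r)L)]. At an illustrative r = 0.05, Cohort 2 would show 32.2% on placebo and 37.5% on vemurafenib, a ratio of 1.16. The ratio is 1.19 at r = 0.01 and 1.14 at r = 0.10.

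**4. Early events.** On the same model, the Cohort 2 difference in time on drug is 3.4% over the first 8 weeks and 4.9% over the first 12. If the 0.05 rate applies only in the first 3 months, the percentages are 13.1% and 13.4%.

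**5. Toxicity stops on vemurafenib.** The documents give no rate for this trial, so these are assumptions: a proportion d stopping by week 52, modelled as an added constant hazard −ln(1 − d)/L. Entries are the placebo shortfall; a negative value means that vemurafenib is observed less.

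| d | Cohort 2 | Cohort 1 | Pooled |
|---|---|---|---|
| 0% | 16.1% | 5.9% | 9.2% |
| 10% | 12.4% | 1.4% | 5.0% |
| 20% | 8.3% | −3.7% | 0.3% |
| 30% | 3.5% | −9.7% | −5.3% |

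Break-even is d = 1 − e^(−(λ_placebo − λ_vemurafenib)L): 36% in Cohort 2 and 13% in Cohort 1.

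**6. Lag from recurrence date to stopping.** SAP 4.4.1 dates recurrence to the scan or examination that prompted biopsy, while drug stops at final diagnosis. An assumed lag of 0.5 to 1 month reduces the Cohort 2 figure to 14.7% to 13.5%.

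**The case against.** The strongest reply is that nothing confirmatory depends on these tables. Safety is descriptive, no between-arm test or ratio is planned, exposure is tabulated by arm, and naming frequency and percentage does not forbid other summaries. That stands as a limit on severity. It does not remove the problem, because a reader will compare the columns and a summary of exposure cannot recover each patient's time at risk to a first event.

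The second reply is that 16% is the largest of three figures and rests on a hazard lasting the whole year. This also stands. Protocol 1.2.5 describes early onset for several known toxicities: a median of 7 to 8 weeks for cuSCC, a median of 44 days for liver injury, and neutropenia often in the first 6 to 12 weeks. For such events the distortion is small.

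Three stronger readings are tempting, and the documents do not support them.

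- *A reader might infer that all safety collection ends at 28 days.* It does not for deaths and serious events believed related, for new primary malignancies, or for cuSCC/KA, so the 16% does not apply to every row of SAP 4.7.2.
- *A reader might infer that the plan hides harm.* On the planned medians the distortion runs against vemurafenib. Understatement would need toxicity stops to dominate, and Protocol 5.1.1 says of earlier studies, "although treatment discontinuation because adverse events has been rare".
- *A reader might infer that one 28-day denominator would repair every table.* It would exclude event time that the protocol deliberately collects: skin examinations at 13 and 26 weeks after last dose, and colonoscopy within 3 months of stopping (Protocol 4.5.2.2). Nor does a rate suit a worst laboratory grade, which is a per-patient maximum set against baseline.

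**Conclusion.** The point holds for ordinary on-treatment adverse events. As planned, the by-arm percentages combine event rate with an observation window that depends partly on recurrence, and no summary separates the two. The expected placebo shortfall is about 16% in Cohort 2, 6% in Cohort 1 and 9% pooled. Those figures assume exponential DFS, the planned treatment effect, drug stopping on the recurrence date and no toxicity stops. Relaxing the last two shrinks the gaps, and enough toxicity stops would reverse them. Protocol version 10 reports that a Cohort 2 DFS benefit was not demonstrated, so the actual gap may differ from the planned one; the documents give no observed durations. The distortion matters mainly for events that accrue through the year. Because its direction depends on stopping rates that the plan cannot know in advance, a time-at-risk summary is a worthwhile addition. It is an improvement to safety reporting and leaves the efficacy conclusions untouched.

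**What to change.** In SAP 4.7.2, keep the crude percentages and add the following by arm, for each cohort and pooled.

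- **Rates.** First events per 100 patient-years, with time at risk from first dose to first event or 28 days after last dose. Apply them to all adverse events, serious adverse events, Grade 3 or higher events and events leading to discontinuation.
- **Fixed early time.** For the main events, cumulative incidence at a time such as Week 12. On the planned medians, about 78% of placebo and 87% of vemurafenib patients in Cohort 2 are still recurrence-free then.
- **Events collected for longer.** For cuSCC/KA, gastrointestinal polyps and new primary malignancies, define a time at risk that matches each event's own protocol collection period.
- **Laboratory data (SAP 4.7.4).** Keep the worst-grade table against baseline. If a time-based summary is wanted, add time to first Grade 3 or higher value; do not compute a rate for worst grade.

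The cost is some SAP wording and a few extra tables from dates already collected, with no new visits, data or patients. The drawback is that the rates assume a roughly constant hazard, which is why the percentages stay and the fixed-time incidence is added.
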